The recruitment (or pre-baseline) visit will be used as an opportunity to screen the clients. Once the client is found to meet the initial eligibility criteria, s/he will be given a MEMS cap, which will be used to track baseline adherence and study eligibility for approximately one month. In case their clinic visit does not coincide with the expected study visit, participants will be provided a study visit appointment and will be told that they will receive travel compensation for making the additional trip. Clients will also be consented to participate during this initial recruitment visit.

Months 1-3 Visits

During the three-month intervention period, participants will be scheduled for monthly clinic appointments and the study coordinators will a) collect information on changes or degradations of existing routine behaviors; b) conduct prize drawings with the *Incentive* group; and c) update contact information in case phone numbers or addresses have changed. After the first three months, this information will be collected during the participants' regular clinic visits. When participants report the degradation of their selected behavioral anchor, a new daily routine will be identified for the anchoring strategy from the suggested list of three common routine behaviors.

Post-Intervention Surveys

Follow-up surveys will be administered at month three (i.e., at the end of the intervention) and month nine (i.e., six months after the end of the intervention) to evaluate behavioral persistence. These surveys will be designed to evaluate how the intervention affects both the primary outcomes and secondary outcomes, as well as cognitive and motivational factors that may be influenced by the intervention. Intervention effects over the nine-month study period will also be assessed as these effects might be most pronounced in the first months when the pill-taking routine is first established but then taper off as the novelty of the intervention fades or anchoring routines are changed. The post-intervention assessment will happen during a scheduled hospital visit to avoid participants having to make costly additional hospital visits specifically for interviews.

Data Collection Methods

Surveys

The baseline survey contains questions pertaining to:

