MEMS-data will be collected continuously over the course of the three-month intervention period allowing for mean adherence assessment during the intervention period. Specifically, the number of pill bottle openings detected by the MEMS cap will be used as a measure of each participant's pills taken per day. Mean adherence will then be calculated as the number of pills taken per day during the intervention period, divided by the number of pills prescribed during the intervention for a given participant (i.e., # of actual bottle openings / # of prescribed bottle openings). This mean adherence measure will be capped at 100%, meaning that any pill bottle openings over the participants' number of prescribed daily pills will be ignored. In this way, the mean adherence measure will range from 0 to 100 and will be calculated for each participant on each day of the intervention period. Only one of the daily ART medication doses will be used to calculate the primary mean adherence variable. Both the mean adherence over the three-month intervention and a monthly measure of mean adherence will be calculated and analyzed.

Primary Outcome 2: Electronically measured mean medication adherence post-intervention

Post-intervention, MEMS data will be collected continuously for six months to investigate post-intervention mean ART adherence ('persistence'). The calculation of this outcome is the same as that of *Outcome 1* except for the timeline over which the data will be collected and analyzed.

Primary Outcome 3: Routinization of ART adherence during intervention

In addition to *Outcomes 1 and 2*, a novel measure of routine adherence will be assessed during the intervention period. The novelty of the measure is in that it is explicitly based on the temporal pattern of pill-taking. The measure will be calculated as the fraction of scheduled pills taken within a two-hour window (+/- one hour) around the typical time that participants report completing their existing routine behavior that anchors their pill-taking. This measure provides an objective way for determining the behavioral automaticity of pill-taking, and will be calculated as the mean of all prescribed pills taken around participants' anchor time over the three-month intervention.

Primary Outcome 4: Routinization of ART adherence post-intervention

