Feasibility and acceptability will be analyzed using summary statistics derived directly from our self-reported measures. To estimate preliminary efficacy, statistical analyses comparing group-level differences in the secondary and tertiary outcome measures will be performed. An Analysis of Covariance framework will be used to test for group differences in each secondary and tertiary outcome, controlling for the participant characteristics that are found to differentiate the groups at baseline. For analyses of dichotomous variables, such as viral suppression, a non-parametric McNemar's test and an analogous multiple logistic regression will be used to control for covariates to assess group differences. In addition to static comparisons of group means for each outcome at three-month intervals, the longitudinal nature of the data will be leveraged by using repeated measures and time-series techniques. Specifically, a linear mixed model with repeated observations will be fit using maximum likelihood through 'xtmixed' in the

software package Stata to study group-level temporal dynamics in daily measures of the primary and secondary outcomes.

Sample and Effect-size Estimation

We will recruit a total of 150 participants and will assume a 90% retention rate through the 9-month study period. This is a conservative estimate of attrition, as previous research in the same clinic and with a similar population observed only 6% attrition over 12-month study periods [44,48]. Given the study objectives of establishing acceptability, feasibility, and preliminary effectiveness, the targeted sample size may not have the power to detect many of the effects that would be clinically significant. Nonetheless, effect size calculations associated with 80% power (2-tailed test) with regard to the primary outcomes at month nine have been carried out. A recent study conducted at Mildmay suggested that mean ART adherence rates are ~ 75% (SD = 20) as measured by MEMS caps [44]. Using these parameters as estimates of adherence for the control group, and 10% attrition at month nine, a sample size of 150 will provide sufficient power to detect a 9% difference in mean adherence between the pooled intervention groups and the control group (effect size = .47), and a roughly 11% difference in mean adherence between the two intervention groups. This translates to the study being able to detect medium effect sizes.

Qualitative Analysis

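### The mixed model for daily cap data is named without participant slopes, residual correlation or clustered errors; fitted in its basic form, its arm-by-time tests would reject too often

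*Combined protocol and SAP*

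**What the plan says.** Statistical Methods and Analyses plans comparisons of group means at three-month intervals. In addition, "the longitudinal nature of the data will be leveraged by using repeated measures and time-series techniques". The next sentence narrows this to one model: "a linear mixed model with repeated observations will be fit using maximum likelihood", run with Stata's xtmixed, to study "group-level temporal dynamics in daily measures of the primary and secondary outcomes". No section names the random effects, the time function, the residual correlation or the method for standard errors.

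MEMS-cap procedures limits monitoring to one daily dose. Primary Outcome 1 says that "the mean adherence measure will range from 0 to 100 and will be calculated for each participant on each day of the intervention period" and that "This mean adherence measure will be capped at 100" percent. Each participant-day is therefore 0 or 100. Primary Outcome 2 uses the same calculation for the six post-intervention months.

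Two sections bear on whether individual trends differ. Post-Intervention Surveys expects that "these effects might be most pronounced in the first months when the pill-taking routine is first established but then taper off". Comparison to prior work reports that, in the team's earlier study, only participants with timely pill-taking kept high adherence once incentives stopped.

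**The concern.** A participant intercept lets people differ in level but not in trend. With independent residuals and model-based errors, the basic model treats each of about 180 post-intervention days as separate evidence on a person's trend. If some people drift up and others down for reasons unrelated to arm, that drift belongs in the standard error of the arm-by-time term, and this model leaves it out. Day-to-day correlation has the same effect.

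Expected outcomes frames the post-intervention hypotheses as arms maintaining adherence better, which invites a reading of arm-by-time terms. Ordinary person-to-person drift could then pass for a difference in persistence between arms. Dissemination and Future Directions says the findings will feed the design of a larger trial, so a false signal would have a cost even in a pilot.

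**Working it through.** **Plan's own figure.** There is none for the mixed model. The detectable differences in Sample and Effect-size Estimation concern mean adherence and do not bear on this test.

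**Inputs from the documents.**
- Mean adherence 75%, SD 20 (Sample and Effect-size Estimation).
- 150 participants allocated 1:1:1 with 10% attrition: 45 control against 90 pooled intervention.
- Six post-intervention months, taken as 180 days.

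**Assumptions.** Alpha is not stated; two-sided 0.05 is used. The SD of individual change over the window and the day-to-day correlation are not given, so ranges are shown.

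**Closed form (180 days, linear time, no serial correlation).**
1. Variance of a 0/100 variable with mean 75: 75 × 25 = 1,875.
2. Within-person daily variance: 1,875 − 20² = 1,475.
3. Sum of squares of day about its mean: 180 × (180² − 1) / 12 = 485,985.
4. Variance of one person's fitted six-month change that the basic model allows for: 180² × 1,475 / 485,985 = 98.3, an SD of 9.9 points.
5. If true individual change has SD s, the actual variance is 98.3 + s². The inflation factor is F = 1 + s² / 98.3. Arm sizes cancel.
6. Type I error = 2 × [1 − Φ(1.96 / √F)].

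| SD of individual six-month change | F | Type I error |
|---|---|---|
| 0 | 1.00 | 5.0% |
| 5 | 1.25 | 8.0% |
| 10 | 2.02 | 16.8% |
| 15 | 3.29 | 28.0% |
| 20 | 5.07 | 38.4% |

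**Simulation with 0/100 data, 180 days, 45 v 90, no arm effect (1,000 trials each).** At SD 10, 15 and 20 the intercept-only test rejects in 17.0%, 26.4% and 35.0% of trials. A test that takes each participant's slope as the unit rejects in 5.2%, 4.6% and 4.0%.

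**Second simulation, adding serial correlation (1,500 trials per scenario).** The windows are 270 days (whole study) and 90 days (intervention). Correlation is the approximate observed lag-1 value.

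| Slope SD | Lag-1 correlation | Intercept only, 270 days | Intercept only, 90 days |
|---|---|---|---|
| 0 | 0 | 4.5% | 5.7% |
| 10 | 0 | 19.1% | 10.6% |
| 20 | 0 | 43.6% | 22.3% |
| 0 | 0.17 | 12.6% | 10.5% |
| 0 | 0.30 | 17.1% | 17.5% |
| 10 | 0.30 | 30.9% | 22.5% |
| 20 | 0.30 | 46.2% | 27.5% |

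Across all 20 scenarios run, the test based on participant-level slope variance rejected in 4.1% to 5.8% of trials. One simulated data set was also fitted by maximum likelihood. The intercept-only standard error was 2.42, matching the formula used. With a random slope it was 3.21, against 3.17 from the participant-level calculation.

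The first row shows that the 0/100 scale is not the cause: without slope variation or serial correlation, the test on such data stays near 5%.

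**The case against.** The strongest reply is that the plan is silent and rules nothing out. A linear mixed model with repeated observations can include random slopes and correlated residuals, and the preceding sentence mentions time-series techniques. This stands in part. A reader might infer that the plan has chosen an intercept-only model, and the documents do not say so. But they do not commit to anything better. The general phrase is narrowed at once to the one model. The design-effects sentence in Handling Missing Data and Attrition concerns dropout weights, not repeated days within a person.

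A reader might also infer that the trial's whole test of persistence is unsound. That is not supported. Primary Outcomes 2 and 4 measure persistence as participant-level quantities over the post-intervention period, and the mixed model is additional to the comparisons of group means. With one mean per participant, this problem does not arise.

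The size rests on assumed slope variation and correlation. That stands too: the sections quoted make differing trends plausible but do not size them, so inflation to several times nominal is the upper part of an assumed range.

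Finally, retention and viral suppression are end-of-study indicators without daily values, so one might want the secondary outcomes struck from the model sentence. That is unsafe. The same section assigns analysis of covariance to secondary and tertiary outcomes, while Outcomes defines no tertiary ones. The numbering may have shifted, with feasibility counted as primary, and the deletion could then remove the adherence measures themselves.

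**Conclusion.** The concern holds as a gap in specification with a real consequence. If the model is fitted in its basic form, its arm-by-time tests reject too often whenever individual trends differ or days are correlated. For the 180-day window the type I error is about 8% to 38% for slope SDs of 5 to 20 points, and about 5% with neither feature. These figures assume the plan's 75% and SD 20, linear time, complete daily data and alpha 0.05. They are for adherence; the routinization measures would have a different mean and variance. The supplementary arm-by-time tests are the only ones at risk. In a pilot this is modest in weight, but it is cheap to remove.

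**What to change.** State in Statistical Methods and Analyses that:
- the daily model has a stated time function, a participant random intercept and a participant random slope on time, with standard errors clustered on participant. Analysing participant-month adherence with the same clustering is an alternative, though not the same model;
- baseline-month cap adherence is always a covariate. Sampling Strategy already collects it, but the present rule of adjusting for characteristics found to differ at baseline would include it only by chance;
- the model applies to the daily cap-based adherence and routinization measures, Primary Outcomes 1 to 4. The primary, secondary and tertiary labels in this section should be reconciled with those under Outcomes.

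This costs a few lines of text and code, plus wider intervals for the arm-by-time terms. Results says analyses are ongoing, and Randomization and Allocation says the impact analyst is blinded. If that blinding still holds, the specification can be fixed before allocation is revealed.

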We propose to test the intervention “INcentives and ReMINDers to Improve Long-term Medication Adherence” (INMIND) in a pilot, parallel group randomized controlled trial (RCT) at the Mildmay Uganda HIV clinic in Kampala, Uganda with two intervention groups and a control group using an even allocation ratio of 1:1:1 between the three study groups. All participants (including in the control group) will receive information about the importance of behavioral routines, as is part of the standard adherence counseling for treatment initiators at Mildmay Uganda and will create personalized ART adherence anchoring strategies. The first intervention group will additionally receive text message reminders of their anchoring strategy, and the second intervention group will receive both the text message reminders and small incentives conditional on taking ART pills within a time window that corresponds to participants’ personalized anchoring strategy. We hypothesize that the text message reminders and incentives will increase participants’ use of their anchoring strategy, and thus medication adherence will be better maintained after the intervention ends in our two intervention groups relative to the control group. We also expect to see stronger maintenance in the intervention group receiving both reminder messages and incentives than the intervention group receiving only reminder messages.

Methods

Ethics Approval

This pilot RCT has been funded by the National Institutes of Mental Health in the United States (R34MH122331) and approved by the RAND Human’s Subjects Protection Committee (2020-N0632), Mildmay Uganda Research Ethics Committee (MUREC) (0701-2021), as well as the Uganda National Council for Science and Technology (HS128ES). As of February 18, 2022, recruitment was completed.

Study Design

This study will use a three-armed randomized controlled trial (two intervention groups and one control group) with randomization at the individual level. The interventions will be administered for a period of three months from the baseline survey. During the intervention period, MEMS data readings will be collected monthly, wherein prize drawings for eligible participants in the Incentives group will be carried out. Since the population of interest are treatment initiators, the monthly study visits are expected to coincide with the monthly clinic visits as mandated for

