A daily list of expected clients will be generated from the master list for the study coordinators to locate those deemed eligible and who are due for a clinic visit. Once a client is located, a pre-baseline visit will be initiated with the study coordinator approaching the client and inquiring about their interest in participating in an ongoing study. On confirming interest, clients will be taken to a separate study room to verify their eligibility, and to receive their consent to participate. Consented participants will be given a medication event management system (MEMS) cap and instructed to store one of their HIV medications in a pill bottle with the MEMS cap attached. Additionally, they will be given a study appointment after approximately one month of this initial visit for adherence data retrieval and baseline survey administration. The first month of adherence data will be used as a baseline and the intervention will not begin before this follow-up visit.

Inclusion Criteria

The study sample will consist of male and female clients aged 18 and older who have started ART at Mildmay within the preceding three months. Treatment initiation is an important eligibility criterion given the conceptual framework of the pilot, which suggests that habit formation during initiation is a key driver for sustained ART adherence over time. Based on electronic records

data from Mildmay, each month at least 100-150 clients with these characteristics begin treatment at the hospital (for a total of 1,758 in 2018); therefore, a large pool of potentially eligible clients will be available for recruitment. Given the nature of the intervention, inclusion will also require participants to own, or have access to a phone at least five days a week throughout the duration of the intervention, while being willing to receive text messages throughout the intervention period.

Exclusion Criteria

Children under the age of 18 were excluded for two reasons: 1) the pediatric clinic is separate from the main recruitment site (which primarily caters to adult clients), and 2) the intervention might require alteration to account for the specific needs of children and adolescents.

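### The stated detectable differences of 9 points (.47) and roughly 11 points do not follow from the documented inputs; at two-sided 0.05, unadjusted, they are about 10.3 and 11.9 points

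*Combined protocol and SAP*

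**What the plan says.** Sample and Effect-size Estimation describes "effect size calculations associated with 80% power (2-tailed test) with regard to the primary outcomes at month nine". It takes a control-group estimate from an earlier study at the same clinic, "mean ART adherence rates are ~ 75% (SD = 20) as measured by MEMS caps", and says "We will recruit a total of 150 participants and will assume a 90% retention rate through the 9-month study period". From these it concludes that the trial has "sufficient power to detect a 9% difference in mean adherence between the pooled intervention groups and the control group (effect size = .47" and can also detect "a roughly 11% difference in mean adherence between the two intervention groups", and it calls these medium effects. Allocation is given in the trial description that closes the introduction, "using an even allocation ratio of 1:1:1 between the three study groups", and again under Randomization and Allocation.

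No significance level appears anywhere in the document. The power text mentions no covariate adjustment and gives no baseline correlation or R-squared. Two other places bear on the point:

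- Sampling Strategy provides for a pre-intervention month of MEMS monitoring: "The first month of adherence data will be used as a baseline".
- Statistical Methods and Analyses plans an analysis of covariance "controlling for the participant characteristics that are found to differentiate the groups at baseline".

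**The concern.** A detectable difference is fixed by the group sizes, SD, power, alpha and any variance reduction from covariates. The plan gives the first three. With the customary alpha and no adjustment, those inputs give larger differences than the ones printed, so the printed figures either rest on an assumption that was left out or are too favourable.

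This is the plan's only statement of what the trial can detect. The results are meant to inform a larger trial, so anyone interpreting a null or borderline result, or carrying these figures forward, needs to know which assumptions lie behind them.

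**Working it through.** **Inputs.** From the plan: 150 recruited, 10% attrition, 1:1:1, SD 20, 80% power, two-tailed. 150 × 0.90 = 135, or 45 per arm. Pooled intervention vs control is therefore 90 vs 45, and intervention vs intervention is 45 vs 45. Assumed here, because the plan does not say: two-sided alpha 0.05, SD 20 in every arm, no covariate adjustment.

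**Formula (normal approximation).** Detectable difference = SD × √(1/n₁ + 1/n₂) × (z₀.₉₇₅ + z₀.₈₀), with z₀.₉₇₅ + z₀.₈₀ = 1.960 + 0.842 = 2.802.

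- Pooled vs control: 20 × √(1/90 + 1/45) × 2.802 = 20 × 0.1826 × 2.802 = 10.23 points. The noncentral t gives 10.30 (d 0.515).
- Between intervention arms: 20 × √(1/45 + 1/45) × 2.802 = 20 × 0.2108 × 2.802 = 11.81 points. The noncentral t gives 11.94 (d 0.597).

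**Do the printed 9 and .47 agree with each other?** 0.47 × 20 = 9.4, which rounds to 9, so yes.

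**Power at the printed figures (noncentral t, SD 20, 45 per arm).**

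| Difference | Comparison | Power at 0.05 | Power at 0.10 |
|---|---|---|---|
| 9 points (d .45) | 90 vs 45 | 68.7% | 79.0% |
| d .47 (9.4 points) | 90 vs 45 | 72.4% | 82.0% |
| 11 points (d .55) | 45 vs 45 | 73.2% | 82.7% |

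Rounding does not explain the shortfall. The largest values that still round to those printed are d = .4749 (about 9.5 points) and 11.49 points. At two-sided 0.05 they have power of 73.3% and 76.9%.

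**Attempts to recover the printed figures (80% power, noncentral t).**

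| Scenario | Pooled vs control | Between arms | Matches 9, .47 and roughly 11? |
|---|---|---|---|
| As documented, two-sided 0.05 | 10.30 (.515) | 11.94 | No |
| 6% attrition, as in the earlier studies (94 vs 47; 47 vs 47) | 10.08 (.504) | 11.68 | No |
| No attrition (100 vs 50; 50 vs 50) | 9.77 (.488) | 11.32 | Only the 11, and it contradicts the stated 10% |
| Two-sided 0.10 (same as one-sided 0.05) | 9.13 (.456) | 10.57 | The 9, and loosely the 11; not .47 |
| Two-sided 0.05, covariate correlation 0.4 | 9.44 (.472) | 10.95 | All three |

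For the last row, the SD is multiplied by √(1 − 0.4²) = √0.84 = 0.917, giving 20 × 0.917 = 18.3. Then 10.30 × 0.917 ≈ 9.44 and 11.94 × 0.917 ≈ 10.95.

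Solving for alpha instead, unadjusted and at exactly 80% power, gives about 0.086 for d = .47 and 0.081 for 11 points. Neither is a conventional level.

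**Does the planned analysis secure the covariate gain?** A baseline month of MEMS data exists, so a correlation of about 0.4 is plausible. But the ANCOVA adjusts only for characteristics on which the groups turn out to differ. If randomisation balances baseline adherence, that variable stays out of the model and the gain is lost.

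**The case against.** The best opposing case is that this is a reporting gap and not a demonstrated error. Alpha is unstated, a single plausible unstated input recovers all three figures, and the claim that they are too favourable depends on the reader's choice of 0.05 with no adjustment. It stands that the figures are not impossible and that the route used cannot be identified. It does not make the statement right as documented: the inputs given do not deliver the printed differences at 80% power under the usual convention, and whichever route was used, the text needs correcting.

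A second point is that SD 20 is offered only for the control group. Adherence is capped at 100%, so the intervention arms could vary less. With an intervention SD of 15 (normal approximation), the pooled comparison is 2.802 × √(15²/90 + 20²/45) = 9.45 points, close to the printed figure, but the comparison between intervention arms is 2.802 × √(2 × 15²/45) = 8.9 points, far from 11. An intervention SD of 18.4 to 19 gives 10.9 to 11.2 between arms. No single intervention SD fits all three figures. The equal-SD assumption should still be declared.

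Third, the ANCOVA is described for the secondary and tertiary outcomes, while the power statement concerns the primary ones, and a repeated-measures mixed model is planned as well. That is so. It makes the link between the power calculation and any adjusted analysis weaker still, since neither description commits to baseline adherence as a covariate.

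Last, this is a pilot whose size was set for feasibility, acceptability and preliminary efficacy. The plan says power may be inadequate, and no decision rule uses these figures. All of that holds, and it limits the weight of the point. A general caution does not make a specific numerical claim correct.

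**Conclusion.** The concern holds. From the documented inputs, with two-sided 0.05, a common SD of 20 and no adjustment (all three assumed), the statement is too favourable by 10.3 − 9.4 = 0.9 points for pooled vs control (1.3 if the printed 9 is taken literally) and by 11.9 − 11 = 0.9 points between the intervention arms. Power at the printed values is roughly 69% to 73%, not 80%.

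If the calculation used an alpha of 0.10 or a baseline correlation of about 0.4, the figures are approached or recovered, and the fault is that this input was omitted. The documents do not show which applies. The practical effect is moderate: effects of 0.52 and 0.60 can still be called medium.

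**What to change.** State the significance level, the SD assumed in each arm, and whether that SD was reduced for a baseline covariate. Then print the figures that follow:

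- **Two-sided 0.05, unadjusted:** about 10.3 points (0.52) for pooled vs control and about 12 points (0.60) between the intervention arms, with 45 per arm and a common SD of 20.
- **Two-sided 0.10:** say so, and print 9.1 (0.46) and 10.6 (0.53).
- **Baseline-adjusted:** give the assumed correlation (0.4 yields 9.4 and 10.9) and specify an ANCOVA of the primary outcomes that always includes baseline-month MEMS adherence, whether or not the groups differ on it.

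The first two options change wording only. The third also fixes one covariate in the analysis, using data already collected. The document reports data collection complete and analyses ongoing, with the impact analyst to be blinded, so such a change is still feasible but should be dated and described as made after data collection. None of the options alters enrolment or trial procedures.
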